##### **Shipping**

\*All samples should be shipped via overnight express courier in insulated containers with enough dry ice to maintain the samples in a frozen state (if samples are to be shipped frozen). All specimens are to be shipped on either Monday, Tuesday or Wednesday to:

Cancer Pharmacokinetics and Pharmacodynamics Facility  
UPMC Hillman Cancer Center  
[name]  
[name].

##### **Regulations**

Shipment of samples must comply with appropriate regulations as specified by the carrier. At a

NCI Protocol #: 9892

Version Date: January 12, 2023

minimum, all samples must be packaged within two containers with absorbent material between containers to control any spill or leakage. The outer container must be puncture-resistant (e.g. cardboard mailing tube, corrugated cardboard box). A biohazard sticker must be affixed to both the inner and outer containers.

## 9.2 Special Studies

### 9.2.1 F-FDG-PET/CT

#### 9.2.1.1 Subject Preparation

##### Prior to Arrival

- Subjects must fast (except for water) for at least 4 hours before administration of F-FDG for the PET/CT exam.
- Subjects should avoid strenuous exercise for 24 hours before the FDG injection to minimize uptake of the radiotracer in muscles.

##### Upon Arrival

- Upon arrival at the PET facility, confirm subject compliance with pre-procedure instructions, particularly that the fasting requirement was met.
- The subject's weight and height shall be measured and recorded (not verbally relayed by the subject).
- The pre-injection blood glucose level must be < 200 mg/dL (measured ideally within one hour of FDG injection). If the serum glucose is > 200 mg/dL, the study should be rescheduled. The referring physician or primary physician of the subject should be contacted to optimize blood glucose control.
- A large-bore intravenous line (typically, a 20 or 22 gauge angiocatheter) or a butterfly needle in a vein of the participant's arm.
- Prior to positioning the subject on the PET scanner the subjects should be asked to urinate.
- Use of a Foley catheter and a single furosemide administration per institutional policy is permitted.

##### Injection of F-FDG

- The dose of FDG to be administered is 10-20 mCi.
- The exact time of calibration of the dose should be recorded and the exact time of injection noted to permit correction of the administered dose for radioactive decay. In addition, the dose remaining in the tubing or syringe, or that was spilled during injection should be recorded. The injection should be performed through an intravenous catheter.

#### FDG-PET/CT Imaging Procedure

- The time between the injection of FDG and PET emission scan start (tracer uptake time) should begin between 50-70 minutes after injection.
- The injection to start of imaging time for the 3-month post therapy PET/CT scans should be within 10 minutes of that for the baseline study.
- The CT component of the PET/CT study will be performed for attenuation correct and anatomical localization (AC, AL).
- All participants must void prior to imaging to ensure clearance of bladder activity.
- A Foley catheter and a single furosemide administration per institutional policy is permitted.
- Participants will be positioned with their arms above their head or on their chest if unable to keep their arms above the head.

9.2.1.2 Typical acquisition parameters for the low-dose CT scan for attenuation correction should be: kVp = 120; effective mAs = 30–80 (participant dependent); gantry rotation time  $\leq$  0.5 sec; maximum reconstructed width = 3–5 mm without overlap. The parameters should use the standard reconstruction algorithm, without any iodinated intravenous contrast agent. Dilute oral contrast is acceptable, if part of typical institutional practice.

9.2.1.3  $^{18}\text{F}$ -FDG PET/CT Reporting: Images will be evaluated on baseline and 3-month scans qualitatively for focal areas of abnormally increased  $^{18}\text{F}$ -FDG uptake in the primary tumor. This will be performed by visually identifying  $^{18}\text{F}$ -FDG uptake. Assessment of uptake in regional lymph nodes also will be performed by visual inspection. New sites of confirmed  $^{18}\text{F}$ -FDG PET/CT activity at 3-months post therapy will be classified as progressive metabolic disease. Local institution nuclear medicine reports should be submitted (section 12.1). Local institution investigators will resolve discrepancies by teleconference.

9.2.1.4 Semi-quantitative  $^{18}\text{F}$ -FDG PET/CT Reporting of Standardized Uptake Value (SUV): Images will be evaluated quantitatively for abnormally increased  $^{18}\text{F}$ -FDG uptake in the primary tumor by measurement of the maximum standardized uptake value normalized for body mass (SUVmax). As a second metric, SUV normalized by lean body mass (SUL) will be calculated. On the baseline, 3-month scans, the SUVmax and SUL within the primary cancer will be recorded. The PET/CT Form recording this data must accompany pre-therapy and 3-month data submissions. As a secondary analysis, an  $^{18}\text{F}$ -FDG PET/CT post therapy: pre-therapy SUVmax ratio will be calculated. Ratios greater than 1.25 will be classified as progressive metabolic disease. Ratios of 0.76 to 1.25 will be classified as stable metabolic disease. Ratios of 0.34 to 0.75 will be considered partial metabolic response. Ratios lower than 0.33 will be marked as complete metabolic response. Ratios indistinguishable from cardiac or liver blood pool activity because of complete resolution of tumor  $^{18}\text{F}$ -FDG uptake (i.e., a cervix indistinguishable from surrounding normal tissue on post therapy imaging) will be labeled also as quantitative metabolic complete response.

9.2.1.5 Evaluation of  $^{18}\text{F}$ -FDG PET CT Target:

**Complete Response (CR):** A metabolic complete response on PET/CT will be defined as greater than -66% reduction in tumor FDG uptake at sites of abnormal tumor FDG uptake noted on pre-treatment FDG-PET study (considering normal cardiac or liver blood pool).

**Partial Response (PR):** A metabolic partial response on PET/CT will be defined as -25% to -66% reduction in tumor FDG uptake at sites of abnormal tumor FDG uptake noted on pre-treatment FDG-PET study (considering normal cardiac or liver blood pool).

**Progressive Disease (PD):** Progressive metabolic disease on PET/CT is classified as an increase in tumor FDG uptake greater than +25% within the tumor region defined on baseline scan (considering normal cardiac or liver blood pool), or appearance of new FDG uptake in new metastatic lesions.

**Stable Disease (SD):** Stable metabolic response will be defined as a change in tumor FDG uptake by less than +25% (increase) or by less than -25% (decrease) at sites of abnormal tumor FDG uptake (considering normal cardiac or liver blood pool) when compared to pre-treatment FDG-PET study.

Patients with a global deterioration of health status requiring discontinuation of treatment or die without objective evidence of disease progression at that time should be reported to be off study treatment due to “symptomatic deterioration.” Every effort should be made to document the objective progression even after discontinuation of treatment.

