### 3. PATIENT SELECTION

#### 3.1 Eligibility Criteria

3.1.1 Patient has a new, untreated histologic diagnosis of stage IB2 ( $> 5$  cm), II, IIIB, IIIC or IVA squamous, adenocarcinoma, or adenosquamous carcinoma of the uterine cervix or stage II-IVA squamous, adenocarcinoma, or adenosquamous carcinoma of the vagina not amenable to curative surgical resection alone. The presence or absence of lymph node metastasis will be based on pre-therapy F-FDG PET/CT. The patient must be able to tolerate imaging requirements of an F-FDG PET/CT scan.

3.1.2 Age  $\geq 18$  years old.

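### Metabolic complete response is defined by percentage falls at baseline-avid sites, but SUV is specified only for the primary, so a partly resolved node cannot be scored and the SUV-ratio analysis ignores nodes

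*Combined protocol and SAP*

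**What the plan says.** **The response rule.** Section 9.2.1.5, repeated in 11.1.4.3, requires for mCR a "greater than -66% reduction in tumor FDG uptake at sites of abnormal tumor FDG uptake noted on pre-treatment FDG-PET study", taking normal cardiac or liver blood pool into account. The partial, stable and progressive categories are also percentage changes; partial and stable use the same baseline sites.

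**The measurements.** Section 9.2.1.4 confines the quantitative read to the primary tumour: "On the baseline, 3-month scans, the SUVmax and SUL within the primary cancer will be recorded". For nodes, Section 9.2.1.3 says: "Assessment of uptake in regional lymph nodes also will be performed by visual inspection".

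**The ratio categories.** Section 9.2.1.4 adds, as a secondary analysis, a post-to-pre-therapy SUVmax ratio: "Ratios lower than 0.33 will be marked as complete metabolic response". A blood-pool clause also counts as complete, with one example: "a cervix indistinguishable from surrounding normal tissue on post therapy imaging) will be labeled also as quantitative metabolic complete response".

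**The population.** Section 3.1.1 admits stage IIIC and fixes nodal status from the baseline scan: "The presence or absence of lymph node metastasis will be based on pre-therapy" FDG PET/CT.

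**The use.** Section 13.3.4 concludes non-inferiority to a 70% mCR rate, with a 5-point margin and 5% type I error, if at least 23 of 28 patients have mCR. Section 2.4.2 gives the source of the 70%: PET showing no disease either locally or at a distance.

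**The concern.** The rule is quantitative at all the kinds of site that light up at baseline, while the quantitative data are specified for one kind only. Node-positive patients are eligible, so avid baseline nodes are to be expected.

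Persistent nodal uptake after chemoradiation is where the endpoint has to separate response from failure. If a patient's primary has cleared and a node has faded without resolving, the plan gives the local reader neither a nodal percentage nor a visual criterion nor a combining rule. Two sites could classify the same scan differently. If the primary's SUV settles the matter by default, the observed rate is set against a 70% benchmark that was defined more strictly.

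**Working it through.** **1. Passages side by side.** Take a patient with an avid primary and an avid pelvic node at baseline, whose primary SUVmax ratio at 3 months is below 0.33.

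| Node at 3 months | 9.2.1.5 / 11.1.4.3 from the data specified | SUVmax-ratio analysis (9.2.1.4) |
|---|---|---|
| Resolved to background | Complete, by eye through the blood-pool wording | Complete |
| Plainly unchanged | Not complete, by eye | Complete |
| Reduced but still avid | Cannot be scored: a fall above or below 66% needs a nodal value | Complete |
| New avid node | Progressive, by eye (9.2.1.3) | Ratio alone says complete, but the new site makes it progressive |

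The third row is the gap in the main definition. The second row, and the third whenever the node fell by less than 66%, are where the secondary ratio analysis departs from 9.2.1.5. An unchanged or faded baseline node is not a new site and has not risen by more than 25%, so the progression clauses do not correct the ratio result.

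**2. The plan's own cutoff.** Inputs from Section 13.3.4: n = 28, null rate 0.70 − 0.05 = 0.65, one-sided 5%. Exact binomial tails:

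- P(X ≥ 23 | 28, 0.65) = 0.0393, within 5%
- P(X ≥ 22 | 28, 0.65) = 0.0923, above 5%

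So 23 is the smallest valid cutoff and the stated rule reproduces. The scoring gap does not change the cutoff; it changes what counts as an event.

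**3. Illustration of size.** The documents give neither input below, so both are assumptions:

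- q = share of patients who are node-positive
- d = share of node-positive patients whose primary meets mCR while a node does not

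If the all-site rate is 0.65 and every patient is scored on the primary alone, the observed rate is p = 0.65 + q × d.

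| q | d | p | P(X ≥ 23 of 28) |
|---|---|---|---|
| any | 0 | 0.650 | 0.039 |
| 0.30 | 0.05 | 0.665 | 0.055 |
| 0.30 | 0.10 | 0.680 | 0.076 |
| 0.50 | 0.10 | 0.700 | 0.113 |
| 0.60 | 0.20 | 0.770 | 0.350 |

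Even the smallest non-zero case shown passes the stated 5%. The table assumes primary-only scoring throughout, so it bounds the effect for each pair (q, d). Nodes correctly failed by eye would bring the figure back towards 0.039.

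**The case against.** The strongest reply is that the visual nodal read already protects the endpoint. Section 9.2.1.3 covers nodes on both scans, blood pool is part of the definition, and Section 2.4.2 describes complete response as absence of disease. A reader does not need an SUV to see that a node has gone or has not changed. The ratio rule, which ignores nodes, is labelled a secondary analysis. Submitted local reports ("Local institution nuclear medicine reports should be submitted (section 12.1") may contain nodal SUVs. All of this stands, and it narrows the gap to partly resolved nodes and the missing combining rule. It does not close it: no passage requires nodal SUVs, and the definition of a positive lesion in Section 11.1.3 (more than twice surrounding uptake) belongs to the RECIST new-lesion algorithm and is not tied to the metabolic categories.

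A reader might infer more than the documents support:

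- **That mCR is undetermined, or decided by the primary alone, in all node-positive patients.** Resolved and plainly unchanged nodes have a visual route.
- **That the plan requires the fall at every site.** The text says "reduction in tumor FDG uptake at sites of abnormal tumor FDG uptake noted on pre-treatment FDG-PET study". Every site is the natural reading, but it is not stated.
- **That the PET/CT form collects no other uptake values.** The form is not in the documents; only its stated content is known.
- **That the rate is inflated by a known number of points.** Any such figure rests on assumed shares.
- **That the HIV+ and non-HIV+ rates are shown to be distorted.** The same rule applies to both cohorts. A difference would need a different nodal mix, which is not documented, and Section 13.3.4 treats that comparison as exploratory.

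**Conclusion.** The point holds in limited form. The specified data cannot apply the stated percentage rule to a baseline-avid node with reduced but persistent uptake, and nothing says how the visual nodal read combines with the primary's SUV change. Separately, the secondary ratio analysis can label a patient a complete responder when 9.2.1.5 would not.

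Where the primary decides, the error can only be upward, because adding a nodal condition can only remove responders. Its size is unknown. The range of 0.055 to 0.35 for meeting 23 of 28, against 0.039, depends on assumed node-positive and discordance shares and on primary-only scoring for all. mCR is a secondary endpoint, but it carries a formal decision rule under which 22 and 23 responders lead to opposite conclusions, so the scoring should be settled before the data are read.

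**What to change.** - Amend Section 9.2.1.4 and the PET/CT form to record baseline and 3-month SUVmax, with SUL as the second metric, for the primary and each baseline-avid node, or the most avid node in each region.
- State in 9.2.1.5 and 11.1.4.3 that the least-responding baseline-avid site sets the metabolic category, and that uptake at blood-pool level counts as complete at that site.
- Apply the same rule to the SUVmax-ratio categories.

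A lighter alternative is to keep the nodal read visual, but with a written criterion for nodal complete response and a rule for combining it with the primary's result.

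**Cost.** A few more fields read from scans already acquired, a look-back at nodal SUVs for patients already scanned, and possibly a slightly lower mCR rate. The 23-of-28 cutoff is unaffected.

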#### 9.2.1.5.1 Duration of Response

Duration of overall response: The duration of overall response is measured from the time measurement criteria are met for CR or PR (whichever is first recorded) until the first date that recurrent or progressive disease is objectively documented (taking as reference for progressive disease the smallest measurements recorded since the treatment started). The duration of overall CR is measured from the time measurement criteria are first met for CR until the first date that progressive disease is objectively documented.

Duration of stable disease: Stable disease is measured from the start of the treatment until the criteria for progression are met, taking as reference the smallest measurements recorded since the treatment started, including the baseline measurements.

#### 9.2.1.6 Outcome Measure

F-FDG-PET/CT to assess treatment response

#### 9.2.1.7 Assessment

##### 9.2.1.7.1 Method of Assessment

standard of care total body scan (skull base to mid-thigh)

##### 9.2.1.7.2 Timing of Assessment

2 scans: pre-treatment and 3-month post-treatment (90 days +/- 7 days from completion of therapy) for acquiring the scans

#### 9.2.2 Methemoglobin

9.2.2.1 Outcome Measure  
% methemoglobin

9.2.2.2 Assessment of methemoglobin

**9.2.2.2.1 Method of Assessment**

Per institutional clinical chemistry procedures

**9.2.2.2.2 Timing of Assessment**

- On PK days (1, 8) before triapine, 4 h after triapine and the next day before any treatment
- Spot methemoglobin if clinically indicated.

9.2.2.3 Handling of Specimens(s)

Per institutional clinical chemistry procedures. Suggestion: 1-2 mL in heparinized blood gas syringe, analyzed within 30 minutes of being drawn.

## 10. STUDY CALENDAR

Baseline evaluations are to be conducted within 14 days prior to start of protocol therapy. In the event that the patient's condition is deteriorating, laboratory evaluations should be repeated within 48 hours prior to start of protocol therapy. Scans and x-rays must be done ≤4 weeks prior to the start of therapy.

Procedure/Test	Pre-Study	Week 1	Week 2	Week 3	Week 4	Week 5	Week 6	EOT	1mo F/U	3mo F/U	L/T F/U
Informed consent	X										
Demographics	X										
Concurrent meds	X	X	X	X	X	X	X	X	X	X	
Medical history	X										
Current nicotine use status P		X									
Physical exam A,B	X	X	X	X	X	X	X	X	X	X	
Vital signs A,B,Q	X	X	X	X	X	X	X	X	X	X	
Height and Weight A,B	X	X	X	X	X	X	X	X	X	X	
Performance status A,B	X	X	X	X	X	X	X	X	X	X	
CBC w/diff, plts A,B	X	X	X	X	X	X	X	X	X	X	
Serum chemistry A,B,C	X	X	X	X	X	X	X	X	X	X	
PTT/PT/INR D	X										
EKG D	X										
FDG-PET/CT, Whole body	X									X	
MRI, Pelvis E	X									X	
Tumor Measurements	X									X	
Baseline signs & symptoms	X										
Methemoglobin monitoring F		X	X	X	X	X					
Adverse event evaluation		X	X	X	X	X	X	X	X	X	
Triapine IV G		X									
Triapine PO H,I		X	X	X	X	X					
Cisplatin IV J		X	X	X	X	X					
Radiation Therapy H,K		X	X	X	X	X					
Brachytherapy L							X				
Urine or serum B-HCG (WOCBP)	X		X M								
Pharmacokinetic Sampling N		X	X								
Patient Diary Review O		X	X	X	X	X					
Review of disease status and Survival R											X

- A. These procedures do not need to be repeated in Week 1 if done pre-study within 7 days prior to start of protocol therapy.
- B. The procedures must be repeated within 1 day prior to cisplatin each week in Weeks 2-5.
- C. Albumin, alkaline phosphatase, total bilirubin, direct bilirubin, bicarbonate, BUN, calcium, chloride, creatinine, glucose, potassium, total protein, SGOT [AST], SGPT [ALT], sodium, magnesium, phosphorus
- D. Required pre-study, then as clinically indicated
- E. This is optional.
- F. Clinical monitoring required Week 1; as clinically indicated Weeks 2-5 (See Section 5.3.3.1). Monitor the % of methemoglobinemia on specific PK and PD days to correlate effect with exposure (see Section 9.2.2)
- G. Day 1
- H. M-F (except holidays); Oral triapine dosing for Dose Level -2 is M/W/F.
- I. Not on the IV triapine day
- J. Tuesdays (Days 2, 9, 16, 23, 30). Weeks 3-5, cisplatin may be given on Monday or Tuesday.
- K. EBRT make-up is permissible (see Section 5.2).
- L. See Section 5.2.1.2
- M. Pregnancy test for women of childbearing potential (WOCBP) must be repeated within 24 hours prior to Cycle 1 Day 1.
- N. See Appendix B and C for detailed schedule.
- O. Study staff should review the patient medication diary each week.
- P. Current nicotine use status will be collected on C1D1.
- Q. Vital signs will have the following windows: +/- 5m for 60m post-dose and +/-10m for 120 and 180m post.
- R. Long term survival follow up: Follow up for progression and survival status will occur via medical record review or phone call and should occur every 6 months (+/- 2 weeks) for a total of 5 years from the off treatment date.

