### 4.3 Patient Registration

#### 4.3.1 OPEN / IWRS

The Oncology Patient Enrollment Network (OPEN) is a web-based registration system available on a 24/7 basis. OPEN is integrated with CTSU regulatory and roster data and with the LPOs registration/randomization systems or Theradex Interactive Web Response System (IWRS) for retrieval of patient registration/randomization assignment. OPEN or IWRS will populate the patient enrollment data in NCI's clinical data management system, Medidata Rave.

Requirements for OPEN access:

- A valid CTEP-IAM account.
- To perform enrollments or request slot reservations: Must be on an LPO roster, ETCTN Corresponding roster, or Participating Organization roster with the role of Registrar. Registrars must hold a minimum of an Associate Plus (AP) registration type.
- Have an approved site registration for a protocol prior to patient enrollment.

To assign an Investigator (IVR) or Non-Physician Investigator (NPIVR) as the treating, crediting, consenting, drug shipment (IVR only), or receiving investigator for a patient transfer in OPEN, the IVR or NPIVR must list the IRB number used on the site's IRB approval on their Form FDA 1572 in RCR.

Prior to accessing OPEN, site staff should verify the following:

- Patient has met all eligibility criteria within the protocol stated timeframes, and
- All patients have signed an appropriate consent form and Health Insurance Portability and Accountability Act (HIPAA) authorization form (if applicable).

Note: The OPEN system will provide the site with a printable confirmation of registration and treatment information. IWRS system also sends an email confirmation of the registration. You may print this confirmation for your records.

Access OPEN at <https://open.ctsu.org> or from the OPEN link on the CTSU members' website. Further instructional information is in the OPEN section of the CTSU website at <https://www.ctsu.org> or <https://open.ctsu.org>. For any additional questions, contact the CTSU Help Desk at [name] or [[contact]](mailto:[contact]).

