#### **4.4 General Guidelines**

[figure not shown]
Following registration, patients should begin protocol treatment within 7 days. Issues that would cause treatment delays should be discussed with the Principal Investigator. If a patient does not receive protocol therapy following registration, the patient's registration on the study may be canceled. The Study Coordinator should be notified of cancellations as soon as possible.

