## 5. TREATMENT PLAN

ENROLLMENT							
Primary Locally Advanced Cervical or Vaginal Carcinoma							
Treatment Schedule							
Week	Day 1*	Day 2*	Day 3	Day 4	Day 5	Day 6	Day 7
1	EBRT Triapine (IV)	EBRT Triapine (PO) CISPLATIN	EBRT Triapine (PO)	EBRT Triapine (PO)	EBRT Triapine (PO)	OFF DAY	OFF DAY
2	Day 8*	Day 9*	Day 10	Day 11	Day 12	Day 13	Day 14
	EBRT Triapine (PO)	EBRT Triapine (PO) CISPLATIN	EBRT Triapine (PO)	EBRT Triapine (PO)	EBRT Triapine (PO)	OFF DAY	OFF DAY
3	Day 15	Day 16	Day 17	Day 18	Day 19	Day 20	Day 21
	EBRT Triapine (PO)	EBRT Triapine (PO) CISPLATIN	EBRT Triapine (PO)	EBRT Triapine (PO)	EBRT Triapine (PO)	OFF DAY	OFF DAY
4	Day 22	Day 23	Day 24	Day 25	Day 26	Day 27	Day 28
	EBRT Triapine (PO)	EBRT Triapine (PO) CISPLATIN	EBRT Triapine (PO)	EBRT Triapine (PO)	EBRT Triapine (PO)	OFF DAY	OFF DAY
5**	Day 29	Day 30	Day 31	Day 32	Day 33	Day 34	Day 35
	EBRT Triapine (PO)	EBRT Triapine (PO) CISPLATIN	EBRT Triapine (PO)	EBRT Triapine (PO)	EBRT Triapine (PO)	OFF DAY	OFF DAY
Brachytherapy (see Section 5.2)							

[figure not shown]
\*Correlative blood sample collections on these days (see protocol Appendix B and C)

\*\*EBRT make-up is permissible. See Section 5.2

NCI Protocol #: 9892

Version Date: January 12, 2023

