## 5.3 Chemotherapy

### 5.3.1 Cisplatin

Cisplatin will be given by IV infusion at a dose of  $40 \text{ mg/m}^2$  on days 2, 9, 16, 23, and 30 (Tues) for a total of 5 weekly cycles. It will also be permitted to include a 6th cycle of cisplatin during the parametrial boost or any make-up radiation treatment in a sixth week of external beam radiotherapy. Patients will be strongly encouraged to increase oral hydration 24 hours prior and after chemotherapy administration. Normal saline will be infused IV as pre- and post-hydration to cisplatin infusion as per institutional standard protocol and investigator discretion. Standard premedication with antiemetic, steroid, and H2 blocker will be administered as per institution protocol. Cisplatin  $40 \text{ mg/m}^2$  (maximum dose, 70 mg) may be mixed with mannitol 25 g in 1L normal saline, but sites may also follow institutional practice. It will be infused over 60-120 minutes or per institutional protocol. All patients receive weekly cisplatin on this protocol.

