### 5.3.2 Intravenous Triapine

Triapine 50 mg intravenous infusion over 120 +/- 10 minutes is administered once during the study within 90 minutes after pelvic irradiation, on day 1 to obtain PK data. Triapine 50 mg is diluted in 500 mL normal saline or 500 mL 5% dextrose in water and administered using DEHP-free low sorbing infusion set. All patients will receive dexamethasone IV prior to each IV triapine infusion. Premedicate with antiemetic as needed for patients developing nausea or vomiting with a previous dose of triapine.

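### The study calendar marks the repeat pregnancy test under Week 2, but the mark's own footnote requires it in the 24 hours before Cycle 1 Day 1

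*Combined protocol and SAP*

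**What the plan says.** The calendar in section 10 has eleven columns: Pre-Study, Weeks 1 to 6, end of treatment, two follow-up visits and long-term follow-up. The pregnancy-test row is marked under Pre-Study, left blank under Week 1, marked with superscript M under Week 2, and blank after that.

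Footnote M to the calendar says: "Pregnancy test for women of childbearing potential (WOCBP) must be repeated within 24 hours prior to Cycle 1 Day 1".

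Three other places bear on the timing:

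- The schedule table in section 5 puts Days 1 to 7 in Week 1 and Days 8 to 14 in Week 2. Radiation and IV triapine are given on Day 1.
- Footnote P says "Current nicotine use status will be collected on C1D1". The nicotine row is marked under Week 1 only.
- Item 3.1.7 requires a negative urine pregnancy test resulted no more than 7 days before protocol therapy begins. It also requires women of childbearing potential to use two contraceptive methods.

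**The concern.** The grid and its footnote give different times for the same test. The calendar is the table from which sites build visit checklists, and footnote M is the only place in the protocol that asks for this repeat. No other section restates the rule and so corrects someone who follows the column. Nothing elsewhere calls for a pregnancy test in Week 2, so the mark cannot be read as a separate, later test.

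What is at stake is a safety check. Section 3.1.7 describes the drug class and radiation as teratogenic, and the repeat test is meant to give a very recent negative result at first exposure. A test left until Week 2 comes after a full first week of treatment: on the section 5 schedule, five radiation fractions, one IV and four oral triapine doses, and one cisplatin infusion.

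**Working it through.** The plan gives no figure to reproduce. The check sets the places side by side and then counts days.

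**1. Where is Cycle 1 Day 1?** The protocol does not define a cycle for this weekly schedule, but three places agree.

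- Nicotine status is collected on C1D1 (footnote P), and its row is marked only under Week 1.
- Day 1 in section 5 is the first radiation and IV triapine day. Section 5.3.2 says the IV dose is "administered once during the study within 90 minutes after pelvic irradiation, on day 1 to obtain PK data".
- Section 5.3.1 gives cisplatin "for a total of 5 weekly cycles" starting on Day 2, so its first cycle is also in Week 1.

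No reading puts Cycle 1 Day 1 in Week 2.

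**2. Do the marked column and the footnote window overlap?**

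- Footnote M window: from 24 hours before Day 1 up to Day 1.
- Week 2 column: Days 8 to 14, which is 8 − 1 = 7 to 14 − 1 = 13 days after Day 1.

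They do not overlap.

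**3. Could the column position come from the PDF extraction?** The row has all eleven cells: a mark, a blank, a mark with M, then eight blanks. Other rows agree with the text: IV triapine is marked in Week 1 only (Day 1), and pharmacokinetic sampling in Weeks 1 and 2 (Days 1 and 8). A shift in this one row is unlikely but cannot be excluded without the original page.

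**4. How old can the last negative test be at first treatment?**

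| Rule followed | Age of last negative test |
|---|---|
| Footnote M | 0 to 1 day |
| 3.1.7 only | 0 to 7 days |

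The largest difference is 7 − 1 = 6 days. The calendar's general 14-day baseline window is wider, but 3.1.7 is an eligibility criterion and sets the binding limit.

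**The case against.** The strongest reply is that the mark carries superscript M, and footnote M is mandatory and clear. Anyone who reads the footnote will test at the right time. The error does harm only if a site copies the column and overlooks the superscript, and nothing in the documents shows that this has happened. This stands, and it is why the point is small. It does not make the grid correct.

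The conflict also rests on the position of one mark in a table read from PDF. That stands too, to the extent set out in the check, and it is why the original page comes first.

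A reader might infer more than the documents support, in three ways.

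- **That women could start treatment untested.** Not if 3.1.7 is followed. It requires a negative result within 7 days of starting, and its contraception requirement reduces the risk further.
- **That the gap between registration and treatment widens the problem.** Section 4.3.1 has sites verify before enrolment that "Patient has met all eligibility criteria within the protocol stated timeframes", and section 4.4 says "Following registration, patients should begin protocol treatment within 7 days". But the 7-day limit in 3.1.7 runs to the start of therapy, not to registration. A delay after registration cannot make a compliant test older than 7 days.
- **That footnote M must also mention the first radiation fraction.** On Day 1 radiation precedes IV triapine, so a test timed only before the drug could follow the first fraction. Footnote M is not worded that way: it sets the test before Day 1, which already precedes every Day 1 treatment.

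**Conclusion.** The calendar is wrong as written in one cell: a repeat test done in the marked column cannot satisfy the footnote attached to it. This is a minor scheduling inconsistency with a limited safety consequence. A site working from the grid alone could begin treatment on a negative test up to 7 days old, where footnote M intends at most 1 day.

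The 6-day difference is an upper bound. It compares the oldest test each rule allows, and assumes that the site follows 3.1.7 but misses the repeat altogether. The documents do not give the proportion of patients who are of childbearing potential, so no number of affected women can be stated. Nothing in the endpoints, the DLT rules or the sample size depends on this. The conclusion also assumes that the extracted table reproduces the printed column.

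**What to change.** Check the calendar on the original page. If the mark is under Week 2 there, move the X with footnote M to Pre-Study, beside the existing mark. Pre-Study is the simpler choice because the footnote window ends before Day 1 treatment. Week 1 would also do, provided the test is done before any Day 1 treatment, radiation included.

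No change to the wording of footnote M is needed. The cost is one moved mark at the next amendment. It adds no test, because footnote M already requires this one.
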